## 4.3.2. Acceptable Methods of Contraception

Heterosexually active female subjects of childbearing potential must agree to use a highly effective method of contraception for the duration of the study and at least 150 days after the last dose of study treatment. Women should not donate eggs during this period.

Highly effective methods of contraception are those that, alone or in combination, result in a failure rate of <1% per year when used consistently and correctly (ie, perfect use) and include:

- Established use of oral, injected, or implanted hormonal methods of contraception
- Correctly placed intrauterine device or intrauterine system
- Sexual abstinence
- Vasectomized partner

## 4.4. Prohibited Concomitant Medications

The following medications are prohibited during the study (unless utilized to treat a drug-related AE):

- Immunosuppressive agents.
- Any concurrent systemic anti-neoplastic therapy (ie, chemotherapy, hormonal therapy, immunotherapy, or standard or investigational agents for treatment of unresectable or metastatic melanoma).
- Any non-palliative radiation therapy.
- Any complementary medications (eg, herbal supplements or traditional Chinese medicines) intended to treat the disease under study.
- Any live/attenuated vaccine (eg, varicella, zoster, yellow fever, rotavirus, oral polio, and measles, mumps, rubella [MMR]) during treatment and until 100 days post last dose.
- Concurrent anticancer therapy with agents other than the combination drug therapy (CMP-001 or nivolumab) is not allowed at any time during the study.

- Chloroquine, hydroxychloroquine, and quinacrine, as these agents are known to have significant TLR9 antagonism.
- Systemic pharmacologic doses of corticosteroids greater than the equivalent of 10 mg/day prednisone are not permitted at the time of study enrollment with the following exceptions:
  - Allowed for subjects with a history of adrenal insufficiency. Consultation with the Medical Monitor is required prior to enrollment of subjects with a history of adrenal insufficiency;
  - Allowed for the management of immune-mediated toxicities;
  - Allowed for palliation of pain, brain metastases, or other disorders if subjects remain on study based on Investigator's judgement after consultation with Medical Monitor.
- Medications intended solely for supportive care (ie, antiemetics, analgesics, megestrol acetate for anorexia) are allowed.

Palliative radiotherapy or palliative surgery (ie, for pain, bleeding, spinal cord compression, brain metastasis, new or impending pathologic fracture, superior vena-cava syndrome, or obstruction) may be allowed after Medical Monitor consultation to ascertain whether clinical progression has occurred. If the lesion(s) targeted for palliation are target lesions, then the anatomic site requiring palliation must be assessed for disease status.

Given the potential for injection site reactions and flu-like symptoms, vaccination with a viral vector or mRNA vaccine should not be performed within 48 hours of CMP-001 injection.

## 4.5. Treatment Discontinuation

Treatment discontinuation is defined as any subject who stops receiving study treatment and does not restart within 12 weeks. Subjects who permanently discontinue (for >12 weeks) CMP-001 or nivolumab may not be re-treated with the discontinued study treatment in this study. When nivolumab is permanently discontinued due to an immune related AE, CMP-001 must also be permanently discontinued.

Treatment with study treatment should continue until one of the following occurs:

- Unacceptable AE that precludes further study treatment
- 2 years of study treatment
- PD per RECIST v1.1; continuation of treatment through suspected pseudoprogression is permitted at the Investigator's discretion until confirmed PD per iRECIST
- Upon request of the Sponsor or regulatory agency
- Clinical disease progression in the opinion of the Investigator
- If medically necessary in the opinion of the Investigator
- Subject withdraws consent for study treatment
- Subject has received study treatment for 2 years
- Subject becomes pregnant or begins breastfeeding

- Subject is lost to follow-up
- Death
- End of Clinical Trial

If a subject achieves and maintains a confirmed CR or iCR by Investigator assessment, IT or SC injections of CMP-001 or the combination of CMP-001 and nivolumab may be discontinued at the Investigator's discretion once the subject meets both of the following criteria:

- Subject has been treated for at least 48 weeks (the maximum duration of study treatment is 2 years)
- Subject has received at least 3 doses of assigned treatment beyond the date of the initial CR/iCR

Subjects with PD per RECIST v1.1 as determined by Investigator assessment should remain on treatment and have a follow-up scan performed at least 4 weeks after the initial date of PD to confirm progression per RECIST v1.1 by BICR.

Subjects who discontinue study treatment should complete an EOT visit and 100-day safety follow-up contact, which should occur 100 days (+7) after the EOT or until an alternative cancer treatment is initiated, whichever occurs first (Table 1). Subjects who discontinue study treatment for reasons other than disease progression (either per RECIST v1.1 or iRECIST by Investigator assessment) should remain on study for PTFU (Section 7.6) and receive disease assessments according to the Schedule of Assessments (Table 1).

# 4.6. Study Discontinuation

Subjects may withdraw from the study at any time without penalty or loss of future medical care or any other benefits to which they are otherwise entitled. Subjects will be withdrawn from the study for any of the following reasons:

- Subject withdraws consent for the study
- Subject lost to follow-up
- Death
- End of Clinical Trial

Subjects who withdraw consent from overall study participation (not only study treatment) will not have the EOT visit, safety follow-up visits, or further evaluations performed.

### 4.7. End of Clinical Trial

The End of Clinical Trial is defined as the last visit for the last subject on the trial.

## 5. TREATMENT OF SUBJECTS

# **5.1.** Administration of Study Treatment

#### 5.1.1. Nivolumab

Subjects will receive CMP-001 10 mg IT injection followed by nivolumab 360 mg IV (Arm A) or nivolumab 360 IV monotherapy (Arm B) at W1D1 and Q3W thereafter until the subject satisfies a condition for study treatment discontinuation. Nivolumab should be administered to the subject according to the nivolumab Investigator's Brochure. Nivolumab should be administered until the subject satisfies a condition for study treatment discontinuation (Section 4.5.). On visits where both study treatments are administered, nivolumab should be administered after CMP-001. There is no specified waiting period between the end of CMP-001 administration and the initiation of nivolumab infusion.

Subjects should receive nivolumab at a dose of 360 mg as a 30-minute infusion each treatment cycle until progression, unacceptable toxicity, withdrawal of consent, or the study ends, whichever occurs first.

There will be no dose escalations or reductions of nivolumab allowed. Subjects may be dosed no less than 19 days from the previous dose.

Subjects should be carefully monitored for infusion reactions during nivolumab administration. If an acute infusion reaction is noted, subjects should be managed according to Section 5.1.4.

Doses of study treatment(s) may be interrupted, delayed, or discontinued depending on how well the subject tolerates the treatment. Dosing visits are not skipped, only delayed.

The assessment for discontinuation of nivolumab should be made separately from the assessment made for discontinuation of CMP-001. If discontinuation criteria are met for CMP-001 but not for nivolumab, treatment with nivolumab may continue if CMP-001 is discontinued.

Please refer to the nivolumab Investigator's Brochure and/or Pharmacy Manual for further details regarding storage, preparation, and administration of nivolumab.

Care must be taken to assure sterility of the prepared solution as the product does not contain any antimicrobial preservative or bacteriostatic agent.

#### **5.1.1.1.** Nivolumab Dose Selection

The nivolumab dose of 360 mg Q3W was selected based on clinical data and modeling and simulation approaches using population pharmacokinetics (PPK) and exposure-response (ER) analyses of data from studies in multiple tumor types (melanoma, NSCLC, and RCC) where body weight normalized dosing (mg/kg) was used.

Nivolumab pharmacokinetics (PK) have been extensively studied in multiple tumor types, including melanoma, NSCLC, RCC, cHL, SCCHN, CRC, and urothelial carcinoma and has been safely administered at doses up to 10 mg/kg Q2W. Nivolumab monotherapy was originally approved as a body-weight based dose of 3 mg/kg Q2W and was updated to 240 mg Q2W or 480 mg Q4W in multiple indications nivolumab Investigator's Brochure. Nivolumab 360 mg Q3W is also under evaluation in monotherapy and in combination therapy studies. Less frequent 360 mg Q3W and 480 mg Q4W dosing regimens can reduce

the burden to subjects of frequent, lengthy IV treatments and allow combination of nivolumab with other agents using alternative dosing regimens.

The benefit-risk profiles of nivolumab 240 mg Q2W, 360 mg Q3W, and 480 mg Q4W are predicted to be comparable to 3 mg/kg Q2W. This assessment is based on a comprehensive characterization of nivolumab PK, safety, efficacy, and ER relationships across indications. Population PK (PPK) analyses have shown that the PK of nivolumab is linear with proportional exposures over a dose range of 0.1 to 10 mg/kg; no clinically meaningful differences in PK across ethnicities and tumor types were observed. Using the PPK model, the exposures following administration of several dosing regimens of nivolumab administered as a flat dose were simulated, including 240 mg Q2W, 360 mg Q3W, and 480 mg Q4W. The simulated average serum concentration at steady state following administration of nivolumab 360 mg Q3W and 480 mg Q4W are predicted to be similar to those following administration of nivolumab 240 mg Q2W and nivolumab 3 mg/kg Q2W administered to subjects over a wide body weight range (34-180 kg) across tumor types.

Nivolumab ER relationships for efficacy and safety were evaluated for IV nivolumab administered as monotherapy at the dose range of 1 mg/kg Q2W to 10 mg/kg Q2W. Generally a flat ER relationship was observed over this dose range in melanoma, RCC, and NSCLC subjects between nivolumab exposure and clinical endpoints such as the hazard of death, probability of overall response, AE leading to discontinuation or death, Grade 3 or higher AEs, and/or Grade 2 or higher immune-mediated AEs. Therefore, 3 mg/kg IV Q2W was approved in melanoma, RCC, and NSCLC and was also studied and approved in other indications. For NSCLC, there was a trend of additional benefit (especially in ORR) at 3 mg/kg IV Q2W when compared to 1 mg/kg IV Q2W, which had a small sample size. Therefore, a flat ER relationship could only be confirmed from 3 mg/kg IV Q2W to 10 mg/kg IV Q2W for NSCLC. Flat doses of 240 mg IV Q2W nivolumab, 360 mg IV Q3W nivolumab, and 480 mg IV Q4W nivolumab have been incorporated in monotherapy and combination oncology studies, and the 240 mg IV O2W and 480 mg IV O4W nivolumab dose regimens are now approved in multiple indications. Every 4 week (Q4W) dosing regimens can reduce the burden to subjects of frequent, lengthy IV treatments and allow combination of nivolumab with other agents using alternative dosing regimens.

Extensive ER analyses using multiple PK measures (maximum serum concentration in Cycle 1, average serum concentration at Day 28 [ $C_{avg28}$ ], and trough serum concentration at Day 28 [ $C_{min28}$ ]) and efficacy and safety endpoints indicated that the efficacy of the flat-dose 480 mg IV regimen is similar to that of 3 mg/kg IV Q2W. In ER efficacy analyses for OS and ORR conducted in melanoma, RCC, and NSCLC using  $C_{avg28}$  as the driver of efficacy, probabilities of achieving a response and survival probabilities at 1 year and 2 years for 480 mg IV Q4W were similar to that of 3 mg/kg IV Q2W.

Similar analyses conducted in different tumor types using the  $C_{min28}$  as the worst-case scenario for the potential loss of efficacy also showed benefit risk profiles of 480 mg IV Q4W were comparable to 3 mg/kg IV Q2W.

## **5.1.1.2.** Clinical Pharmacology Summary

Nivolumab PK was assessed using a PPK approach for both single-agent nivolumab and nivolumab with ipilimumab.

*Nivolumab as a single agent:* The PK of single-agent nivolumab was studied in patients over a dose range of 0.1 to 20 mg/kg administered as a single dose or as multiple doses of nivolumab as a 60-minute IV infusion Q2W or Q3W. Nivolumab clearance (CL) decreases

over time, with a mean maximal reduction (% coefficient of variation [CV%]) from Baseline values of 24.5% (47.6%) resulting in a geometric mean steady-state clearance (CLss) (CV%) of 8.2 mL/h (53.9%) in patients with metastatic tumors; the decrease in CLss is not considered clinically relevant. Nivolumab clearance does not decrease over time in patients with completely resected melanoma, as the geometric mean population clearance is 24% lower in this patient population compared with patients with metastatic melanoma at steady state. The geometric mean volume of distribution at steady state (CV%) is 6.8 L (27.3%), and geometric mean elimination half-life (CV%) is 25 days (77.5%). Steady-state concentrations of nivolumab were reached by 12 weeks when administered at 3 mg/kg every 2 weeks, and systemic accumulation was 3.7-fold. The exposure to nivolumab increased in a dose proportional manner over the dose range of 0.1 to 10 mg/kg administered Q2W. The predicted exposure (average serum concentration and maximum serum concentration) of nivolumab after a 30-minute infusion is comparable to that observed with a 60-minute infusion.

Specific Populations: The PPK analysis suggested that the following factors had no clinically important effect on the CL of nivolumab: age (29 to 87 years), weight (35 to 160 kg), gender, race, Baseline lactate dehydrogenase PD-L1 expression, solid tumor type, tumor size, renal impairment, and mild hepatic impairment.

Renal Impairment: The effect of renal impairment on the CL of nivolumab was evaluated by a PPK analysis in patients with mild (estimated glomerular filtration rate [eGFR] 60 to 89 mL/min/1.73 m^2), moderate (eGFR 30 to 59 mL/min/1.73 m^2), or severe (eGFR 15 to 29 mL/min/1.73 m^2) renal impairment. No clinically important differences in the clearance of nivolumab were found between patients with renal impairment and patients with normal renal function.

Hepatic Impairment: The effect of hepatic impairment on the CL of nivolumab was evaluated by population PK analyses in patients with HCC and in patients with other tumors with mild hepatic impairment (total bilirubin [TB]  $\leq$  ULN and AST > ULN or TB > 1 to 1.5  $\times$  ULN and any AST) and in HCC patients with moderate hepatic impairment (TB > 1.5 to 3  $\times$  ULN and any AST). No clinically important differences in the clearance of nivolumab were found between patients with mild/moderate hepatic impairment.

Details on the clinical pharmacology aspects of nivolumab can be found in the nivolumab Investigator's Brochure.

#### 5.1.2. CMP-001

Subjects randomized to Arm A will receive CMP-001 10 mg weekly for 7 doses (W1D1 to W7D1), after which CMP-001 will be administered by IT injection Q3W (W10D1, W13D1, etc.). The first dose of CMP-001 may be administered SC or by IT injection, at the discretion of the Investigator; all subsequent doses are planned to be administered IT. The initial 7 CMP-001 weekly dose schedule must be completed before starting the Q3W CMP-001 dosing schedule.

On visits where both CMP-001 and nivolumab are administered, CMP-001 should always be administered before nivolumab. There is no waiting period between the end of CMP-001 administration and the initiation of nivolumab infusion.

CMP-001 should be administered until a reason for treatment discontinuation is reached (Section 4.5).

See Section 5.1.3 for dose modifications for CMP-001.

## 5.1.2.1. Prophylaxis Prior to CMP-001 Injection

To prevent or reduce the severity of symptoms associated with CMP-001 administration, prophylaxis is required. Institutional regimens for prophylaxis related to cytokine release may be followed but only after discussion with the Medical Monitor; otherwise, the recommended regimen should be completed prior to initiation of CMP-001 injections:

- Intravenous fluids (eg, approximately 500 to 1000 cc IV normal saline; the volume is at the Investigator's discretion)
- Antipyretics (eg, acetaminophen 1000 mg and a non-steroidal anti-inflammatory agent such as indomethacin 50 mg or ibuprofen 600 to 800 mg)
- Antiemetics (eg, oral ondansetron 8 mg)
- Antihistamine (eg, oral diphenhydramine 50 mg, with or without an H2-antagonist)
- Recommended: hydrocortisone 25 mg at the Investigator's discretion. Subjects with adrenal insufficiency should be treated with stress dose steroids as described in Section 5.1.2.1.1.

Maintenance IV fluids should be continued after the CMP-001 injection during the observation period for continued fluid administration to minimize the risk for hypotension. Antipyretics and antiemetics may be repeated at the Investigator's discretion. There is no waiting period between the end of prophylaxis and the start of the CMP-001 injection. All treatments given prophylactically before and after CMP-001 dosing must be recorded for each visit.

## 5.1.2.1.1. Prophylaxis for Subjects with a History of Adrenal Insufficiency

Subjects with a history of adrenal insufficiency are at increased risk for moderate to severe AEs, such as hypotension, which may occur within 1 to 4 hours after CMP-001 injection but may also occur outside this window. These subjects must receive stress dose steroids (eg, 50 mg to 100 mg hydrocortisone or equivalent orally every 8 hours) before and for 24 to 48 hours after each CMP-001 injection.

## 5.1.2.2. Observation Following CMP-001 Dosing

Subjects must be observed for at least 4 hours following each of the first 6 CMP-001 injections (W1D1 to W6D1). Beginning with the seventh CMP-001 injection (W7D1), the observation period may be reduced to a minimum of 1 hour following CMP-001 injection at the Investigator's discretion based on the AE profile of the individual subject.

## **5.1.2.3. CMP-001 Injections**

## **5.1.2.3.1.** Injectable Tumor Selection

Eligible subjects must have at least 1 accessible lesion amenable to repeated IT injection. Cutaneous, SC, and/or nodal tumors that are visible, palpable, or detectable by ultrasound guidance are acceptable for IT injection. Tumors should be at least 0.5 cm in longest diameter and need not be the largest lesion. The preferred tumor for IT injection is an accessible lesion that is most rapidly progressing in the judgment of the Investigator.

When more than 1 tumor is amenable to IT injection, the Investigator may inject up to 3 tumors per CMP-001 treatment visit. The total dose of CMP-001 may be divided across the

tumors at the Investigator's discretion, and the volume injected into each tumor must be recorded. The same tumor(s) should be injected each week during therapy, if possible. If an injected tumor is clearly decreasing in size and another accessible non-injected tumor is not, then the Investigator may divide the CMP-001 dose between the 2 tumors or switch from injecting the regressing tumor to injecting the non-responding (or growing) tumor. However, there should always be at least 1 target lesion measuring 1 cm or more in diameter that will not be injected for each subject. These lesions not intended for injection may be located in any metastatic site.

Subjects with metastatic disease who have regression of all injectable lesions, or who have an injection site reaction that precludes injection of the tumor, should receive CMP-001 SC near an original tumor (peritumoral) or in the area of the draining lymph nodes (see Appendix G).

#### 5.1.2.3.2. Method of CMP-001 Administration

Topical or local anesthesia may be used at the Investigator's discretion.

Syringe size is at the discretion of the Investigator or qualified designated staff for administering the CMP-001 study drug according to institutional guidelines or standard operating procedures (SOPs). For methods of CMP-001 administration, see Appendix G.

## 5.1.3. Dose Modifications and Management of CMP-001 Associated Adverse Events

Based on earlier studies of CMP-001, CMP-001—associated adverse events such as injection site reactions and flu-like symptoms may occur within hours following CMP-001 injection. Guidance for the observation period following CMP-001 injection is provided in Section 5.1.2.2. CMP-001 is a TLR9 agonist designed to activate pDCs, which secrete IFN and activate other immune cells to produce IFN-associated T helper cell Type 1-promoting cytokines and chemokines. Therefore, it is expected that the AE profile associated with CMP-001 injection may be similar to that observed after systemic administration of IFNs. These AEs may be observed with any injection and could occur outside of the observation window following an injection. More information can be found in the CMP-001 Investigator's Brochure.

The CMP-001 dose should remain unchanged during the study, unless deemed medically necessary by the Investigator after discussion with the Medical Monitor.

If a planned dose cannot be administered on schedule due to a CMP-001 related toxicity, the injection should be delayed until the toxicity has improved or resolved. When nivolumab dosing is held or delayed, CMP-001 dosing must also be held or delayed. If a subject has CMP-001 dosing withheld for more than 3 consecutive doses for any reason during the Q3W dosing period, resumption of treatment must be discussed with the Medical Monitor, otherwise, the subject will be discontinued from study treatment and will have all EOT assessments performed.

If a planned nivolumab dosing is delayed, the CMP-001 dosing may also be delayed.

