Abbreviations: 100DFU = 100-day follow-up; AE= adverse event; CNS = central nervous system; CR = complete response; CT = computed tomography; D/d = day; ECG = electrocardiogram; ECOG = Eastern Cooperative Oncology Group; EOT = End Of Treatment; FSH = follicle stimulating hormone; iRECIST = immunotherapy Response Evaluation Criteria in Solid Tumors; iCR = immune complete response; INR = international normalized ratio; iPR = immune partial response; IT = intratumoral; LTSFU = Long-Term Survival Follow-up; MRI = magnetic resonance imaging; N/A = not applicable; PD-L1 = programmed cell death protein ligand 1; PET = positron emission tomography; PR = partial response; PT = prothrombin time; PTFU = Post-treatment Follow-up; PTT = partial thromboplastin time; RECIST = Response Evaluation Criteria in Solid Tumors; Q3mo = every 3 months; Q3W = every 3 weeks; Q6W = every 6 weeks; SC = subcutaneous; SAE = serious adverse event; W = week; WOCBP = women of child bearing potential.

- a. End of Treatment assessments to be performed within 7 days following subject discontinuation from the last study treatment (either CMP-001 or nivolumab). Removal of a subject from CMP-001 treatment is defined as the time in which the Investigator decides to discontinue study treatment. If a subject has CMP-001 dosing withheld for more than 3 consecutive doses for any reason during the Q3W dosing period, resumption of treatment must be discussed with the Medical Monitor, otherwise, the subject will be discontinued from study treatment and will have all EOT assessments performed.
- b. The 100DFU is a safety follow-up visit that may be conducted at the study site or via phone. This visit should occur 100 days (+7) after the EOT.
- c. Post-treatment Follow-up (PTFU) will be conducted every 3 months (± 2 weeks) for all subjects who discontinue study treatment but have not met criteria for study discontinuation. These subjects should remain on study and receive disease assessments every 3 months, until discontinuation.
- d. Long-Term Survival Follow-up (LTSFU) will be conducted every 3 months (± 4 weeks) after the EOT visit or the last disease assessment date in PTFU and may occur via phone.

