- i. AEs will be assessed continually from the time of informed consent through 100 days after the last dose of study treatment or until an alternative cancer treatment is initiated, whichever occurs first, for all subjects. Subjects who discontinue CMP-001 but remain on treatment with nivolumab will continue to have AEs collected according to this schedule until 100 days after the last dose of nivolumab.
- j. Concomitant medications will be assessed continually from 30 days before the first dose of study treatment through 100 days after the last dose of study treatment or until an alternative cancer treatment is initiated, whichever occurs first. Treatment medications for AEs related to study treatment that occur more than 100 days after the last dose of study treatment will be collected.
- k. 12-lead ECGs will be obtained at Screening, before the W1D1, W3D1, and W7D1 CMP-001 injections, and at EOT. ECG parameters will include heart rate and PR, QRS, QT, and QT corrected for heart rate (using Fridericia's formula) intervals. ECGs will be performed after the subject has been resting in supine or semi-supine position for at least 5 minutes. When an ECG is scheduled at the same time as a blood sampling, the ECG reading should be obtained before the scheduled blood sampling.
- 1. Clinical laboratory assessments may be performed up to 72 hours before the study treatment administration. When clinical laboratory assessments are done the same day as study treatment administration, vital signs should be performed prior to collection of clinical laboratory tests; an extension up to 72 hours prior to the start of study treatment is permissible in situations where results cannot be obtained within the standard 24-hour window. Refer to Section 7.1.12 for Clinical Laboratory Assessments.
- Note: For WOCBP a serum pregnancy test should be done at Screening. Serum or urine pregnancy tests should be done prior to the first CMP-001 injection on W1D1, W4D1, W7D1, Q3W thereafter, and EOT. An FSH test is required at screening to confirm menopause (FSH level >40 mIU/mL) in women <55 years of age (Section 4.3.1). Refer to Section 7.1.13 for Pregnancy Testing.

  Note: Coagulation samples (PT, INR, and PTT) to be collected and results reviewed prior to the W1D1 CMP-001 injection visit and prior to every CMP-001 injection beginning at W7D1 and continuing Q3W thereafter.

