- m. Exploratory biomarker blood samples are to be collected at the following time points during the Phase 2 portion of the study only: W1D1 within 2 hours before CMP-001 injection; W5D1 (same day as tumor biopsy) before CMP-001 injection; W6D1 within 2 hours before CMP-001 injection, 4 hours (± 30 minutes) after CMP-001 injection, and 24 hours (± 4 hours) after CMP-001 injection (W6D2); and W7D1 within 2 hours before CMP-001 injection. Refer to Section 7.3.1 Collection of Blood for Translational Biomarker Analyses.
- n. Fresh tumor biopsy samples are mandatory, if safe and medically feasible, at Screening (before W1D1) and W5D1 (±1 week) prior to CMP-001 IT injection. If the Investigator believes it is unsafe to perform a biopsy, the subject may be considered eligible after discussion with the Medical Monitor if tissue and/or prior assessments are available to determine PD-L1 expression. Archival tumor biopsy samples should also be collected during Screening, if available. Refer to Section 7.3.2 for Tumor Biopsies.
- o. Disease Assessment methods include radiographic (contrast-enhanced CT alone or in combination with PET or MRI), photographic, and CNS imaging by contrast-enhanced CT or MRI (per site local standards). The same modality used at Screening must be used throughout the study. Disease assessments will be performed predose beginning at W10D1 (-7 days) and repeated every 6 weeks (-7 days) (eg, W16D1, W22D1, etc). A response (CR, PR, iCR or iPR [per RECIST v1.1 or iRECIST]) will be confirmed with follow-up disease assessments performed at least 4 weeks after the date of initial response. Disease assessments will continue every 6 weeks after the confirmatory scans. All scans should be performed at least 2 weeks after a previous CMP-001 IT injection to prevent injection-related pseudoprogression. Disease assessments will be performed every 12 weeks for subjects continuing on study more than 1 year. Refer to Section 7.2 for Disease Assessments.
- p. Baseline CNS imaging by contrast-enhanced CT or MRI must be provided at Screening; on-study CNS imaging is required only if symptoms or history of CNS disease is present at Baseline.

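### Protocol 5.1.3 and Table 1 note a: a lapse in CMP-001 dosing ends 'study treatment', which read literally also stops nivolumab and so conflicts with Section 5.1.1

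*Protocol*

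**What the plan says.** The same sentence stands in Protocol Section 5.1.3 and Table 1 note a. If CMP-001 is withheld for more than 3 consecutive doses in the three-weekly period, whatever the reason, resumption must be discussed with the Medical Monitor; "otherwise, the subject will be discontinued from study treatment and will have all EOT assessments performed".

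Note a also fixes when EOT falls: "End of Treatment assessments to be performed within 7 days following subject discontinuation from the last study treatment (either CMP-001 or nivolumab".

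Section 5.1.1 treats the two drugs differently: "The assessment for discontinuation of nivolumab should be made separately from the assessment made for discontinuation of CMP-001". It adds: "If discontinuation criteria are met for CMP-001 but not for nivolumab, treatment with nivolumab may continue if CMP-001 is discontinued".

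Table 1 note i plans for such subjects: "Subjects who discontinue CMP-001 but remain on treatment with nivolumab will continue to have AEs collected according to this schedule". Sections 7.4 and 7.4.1 say the same. Section 4.5 links the drugs in one direction only: nivolumab stopped for an immune-related AE stops CMP-001.

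For subjects who have stopped treatment before meeting study discontinuation criteria, Table 1 note c says: "These subjects should remain on study and receive disease assessments every 3 months, until discontinuation". On treatment, scans are six-weekly (Section 3.1), and after a year note o applies: "Disease assessments will be performed every 12 weeks for subjects continuing on study more than 1 year".

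**The concern.** The trigger names CMP-001, but what stops is 'study treatment'. Section 7.4 explains that term as both drugs, and the full EOT battery belongs after the last drug. A site that follows the sentence literally would stop nivolumab in a subject who meets no nivolumab stopping criterion.

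Section 1.4.5 says the trial was designed to show what CMP-001 adds to PD-1 blockade, so nivolumab should be managed alike in both arms. This rule can act only in Arm A, because Arm B receives no CMP-001. Under the literal reading the subject could lose an active drug and, in the first year, move from six-weekly to three-monthly scans. SAP Section II.F lets subjects stay on treatment to the two-year cutoff under the current protocol, so closing enrollment did not retire the clause.

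**Working it through.** The plan gives no figure on this point. The check compares the texts and then sizes the literal reading.

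**1. Which drug stops?**
- *Both drugs:* the clause says 'study treatment', which Section 7.4 explains as both; it orders all EOT assessments, and note a ties these to the last drug.
- *CMP-001 only:* the clause sits in the CMP-001 dose-modification section; the resumption it mentions can only be of the withheld CMP-001; Section 5.1.1 separates the decisions.
- Under the second reading a subject still on nivolumab has a full EOT, against note a's own timing. The 100-day contact, counted from EOT, could then fall while nivolumab continues.

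**2. Earliest trigger.** Three-weekly CMP-001 starts at W10. More than 3 means at least 4: W10, W13, W16, W19. The earliest trigger is W19.

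**3. Overlap with Section 4.5.** The last dose is W7, and W7 to W19 is 12 × 7 = 84 days. With windows of ±2 days at W7 and ±3 days at W19 the range is 79 to 89 days, or 11.3 to 12.7 weeks. The next scheduled dose, W22, is 15 weeks after W7. Section 4.5 bars re-treatment with a drug stopped for more than 12 weeks. The two rules are formally separate but fall at almost the same time, and Section 4.5 touches CMP-001 alone.

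**4. Nivolumab doses, upper bound.** Doses at W1 and every 3 weeks within 730 days: the last is W103, so (103 − 1)/3 + 1 = 35. Through W19: (19 − 1)/3 + 1 = 7. Lost: 35 − 7 = 28. This assumes nivolumab would otherwise run for the full two years.

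**5. A more typical loss.** Assume exponential progression from W19 with median *m* and nivolumab stopped at progression. Expected doses forgone = Σ 2^(−3k/m), k = 1 to 28, with *m* in weeks. The medians are from Protocol Section 1.1.
- 4.1 months (17.8 weeks): about 8 doses.
- 6.9 months (30.0 weeks): about 12 doses.
- 11.5 months (50.0 weeks, the PD-1 plus CTLA-4 figure): about 16 doses.

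Treatment beyond progression would raise these; stopping for toxicity would lower them.

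**6. Scans to W52, upper bound.** Six-weekly scans left after W19: W22, 28, 34, 40, 46, 52 = 6. Three-monthly follow-up (13 weeks) from an EOT at W19 to W20: W32–33 and W45–46 = 2.

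**7. Lag in dating progression.** Taking half the scan interval (progression uniform within it): year 1, 6/2 = 3.0 against 13/2 = 6.5 weeks, a difference of 3.5 weeks. After year 1, 12/2 = 6.0 against 6.5 weeks.

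**8. Weight of one subject.** 1/9 = 11% of Arm A (SAP Section II.C: 9 and 11 subjects).

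Under the CMP-001-only reading, no nivolumab dose or scan is lost.

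**The case against.** The strongest reply is that the protocol largely shows what was meant. Besides the placement of the clause, the term is used for a single drug elsewhere. Section 4.5 does so, and note a says: "Removal of a subject from CMP-001 treatment is defined as the time in which the Investigator decides to discontinue study treatment". CMP-001 withholding is not a stopping reason in the Section 4.5 list or in Protocol Table 2, which governs nivolumab. SAP Table 2 refers to end-of-treatment dates and forms in the plural, and SAP Section IX.A.1 computes duration for each drug, which suggests that end of treatment is recorded per drug. This stands as evidence of intent: CMP-001 alone is the more likely meaning. It does not remove the conflict, because no sentence says so and the EOT instruction still points to both drugs.

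The reply is also right that the trigger is narrow. Lesion regression or an injection site reaction leads to subcutaneous dosing (Section 5.1.2.3.1), and a Medical Monitor discussion averts the clause. Even the count is uncertain: Protocol Table 8 defines a withheld dose as skipped, while Section 5.1.1 says visits are postponed rather than missed. Where CMP-001 is held because nivolumab is held, nivolumab's own 12-week limit (Section 5.1.4) already applies in both arms. That limit exempts prolonged steroid tapers. If doses held during a taper count as withheld, an Arm A subject could meet the clause when an Arm B subject on the same taper could not.

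A reader might infer more: that the plan deliberately withdraws nivolumab from Arm A, or that the arm comparison is biased. The documents support neither. No passage shows such a choice. Three-monthly scans apply in both arms to anyone who stops treatment before progression. PFS events count on or off treatment (SAP Section VIII.A). Losing nivolumab could shorten PFS while later detection could lengthen it, so the direction is unknown. No effect on ORR, the primary endpoint, is shown.

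**Conclusion.** The clause is wrong as written, but the point is minor. It is an internal conflict between two stated rules: Section 5.1.3 and Table 1 note a, read literally, stop both drugs, while Section 5.1.1, Table 1 note i and Sections 7.4 and 7.4.1 provide for nivolumab to continue.

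The losses of up to 28 of 35 doses and of scans from 6 to 2 hold only under the literal reading, at the earliest trigger, for a subject who would otherwise complete two years without progression or toxicity. The documents do not say how many subjects are affected; it may be none. With 9 and 11 subjects and exploratory analyses (SAP Sections II.C and VI.I), no formal test is at stake. What matters is that no subject loses nivolumab through loose wording and that the Arm A data can be read cleanly.

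**What to change.** In Section 5.1.3 and Table 1 note a, replace the final clause with: *otherwise, the subject will be permanently discontinued from CMP-001; nivolumab and the on-treatment disease assessment schedule continue unless nivolumab discontinuation criteria are met, and EOT is performed when nivolumab stops.*

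Optionally, flag in the by-subject dosing listing already planned in SAP Section IX.A.3 any Arm A subject whose nivolumab was stopped under this rule.

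The cost is one clause in two places and, if wanted, one flag. It needs no new data items and changes no sample size, power or alpha.
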